### **Data Collection:**

#### **1 Data evaluation (See Case report form)**

#### **2 Interpretation of Anticipated Results:**

### **Statistical analysis**

Differences in strength as measured by dynamometry pre-and post-injection will be assessed by Fishers exact test.

Means and standard deviations of subject demographic data, as well as pain scores and UEFI scores will be calculated.

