**Research Question(s):**

Primary: Does lidocaine versus saline as a steroid diluent affect objective upper extremity strength following cervical epidural steroid injection in patients being treated for cervical radicular pain?

Secondary: Does lidocaine versus saline as a steroid diluent affect short-term pain, function, medication use, and global impression of change outcomes of cervical epidural injection for the treatment of radicular pain?

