**Null Hypothesis:**

1. Cervical epidural steroid injections that include local anesthetic as a diluent have no effect on objective upper extremity strength following the injection.
2. Cervical epidural steroid injections for radicular pain that include lidocaine compared to saline as a diluent do not improve short-term pain, function, medication use, and global impression of change outcomes.

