### **Power Analysis**

Statistical Plan & Sample Size Calculation:

Size of study groups:

Group 1: n = 52

Group 2: n = 52

A power analysis was performed based upon previous observations of UE strength (28) using Fisher's Exact Test. Sample sizes of 52 in each of the two treatment groups will achieve > 80% power to detect a group different in proportions, assuming 20% of patients in the Lidocaine group will demonstrate a motor deficit after the CESI and those in the Saline group will demonstrate no difference in motor strength after the CESI, assuming a 2% measurement error with the strength testing method described. The alpha level of this test statistic is set at 0.05, but the significance level actually achieved by this study design is 0.0004.

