### **Data Analysis Plan**

The primary outcome will be the proportion of participants with 50% or greater reduction in neck and arm pain on the NRS pain score at the 1-month follow-up assessment. Secondary outcomes included reduction in median NRS pain score (both neck pain and arm pain), NDI-5, MQS III, opioid consumption in daily morphine equivalents, PGIC score, and satisfaction score. Secondary outcomes will also be defined based on categorical “responder analysis” definitions of important clinical change given the National Institutes of Health recommendation for responder analysis in the assessment of therapeutic spine pain interventions. The responder analysis will include the proportion of patients with 30% or greater improvement on the NDI-5, a PGIC score less than 3 (indicating “improved” or “very much improved”), a 6.8 or greater point reduction on the MQS III score (equivalent to approximately 10 daily morphine equivalents), and the proportion of participants who undergo surgical spine surgery.

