### **Primary outcome:**

- Change in strength for each individual in each treatment group before and 30 minutes after CESI
- Categorical analysis based on a minimally clinically important change of 19.5% for upper extremity strength assessment (29).

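### The strength analysis is worded as a pre/post Fisher's exact test: name the lidocaine-versus-saline comparison at 19.5%, and add a supporting baseline-adjusted analysis of strength

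*Combined protocol and SAP*

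**What the plan says.** The Statistical analysis section has one sentence on strength: "Differences in strength as measured by dynamometry pre-and post-injection will be assessed by Fishers exact test". It names no arms, threshold, direction or sidedness. The rest of that section promises only means and standard deviations for demographics, pain and UEFI scores.

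Other sections are clearer about the comparison:

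- Research Question(s): "Does lidocaine versus saline as a steroid diluent affect objective upper extremity strength following cervical epidural steroid injection".
- Power Analysis: Fisher's exact test with 52 per group, a size that "will achieve > 80% power to detect a group different in proportions". For the event rates, the section's stated premises are "assuming 20% of patients in the Lidocaine group will demonstrate a motor deficit after the CESI", no true deficit on saline and a 2% measurement error. Alpha is 0.05 nominal and 0.0004 achieved.
- Null Hypothesis, item 1: "Cervical epidural steroid injections that include local anesthetic as a diluent have no effect on objective upper extremity strength following the injection". Saline is not mentioned.

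The Primary outcome section has two bullets. The first is "Change in strength for each individual in each treatment group before and 30 minutes after CESI". The second is a categorical analysis that takes 19.5% as the smallest clinically important change.

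The Procedure section plans four strength tests (grip, wrist extension, elbow flexion, elbow extension) on both sides, before and 30 minutes after injection.

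**The concern.** Three gaps meet in one sentence.

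1. **The comparison.** Fisher's exact test is for independent groups. A literal pre/post version would compare patients with themselves as if they were different people, and would not use the randomisation. A deficit defined as a fall from baseline does not exist at baseline, so the pre/post table could not even be filled in.
2. **The scale.** Fisher's test cannot analyse an uncategorised change. If the two Primary outcome bullets are separate items, the first has no method. If they are one item (change, then categorised), no planned analysis addresses a loss smaller than 19.5%. The Introduction gives mild weakness as a reason for the study, because it could matter when a patient relies on a handrail or cane. A non-significant result at 19.5% could be read as showing no weakness when a smaller general loss had not been examined.
3. **The unit.** No section says how eight measures per patient become one deficit or one strength value. Neither analysis can be run until that is settled, and leaving it open allows the rule to be chosen after the data are seen.

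**Working it through.** **Step 1. Reproduce the plan's figure.** Inputs from Power Analysis: n = 52 per arm, 20% on lidocaine, 2% on saline (the measurement error read as a rate), alpha 0.05. Power is the sum, over all pairs of counts (i, j) for which the two-sided Fisher p is at most 0.05, of Bin(i; 52, 0.20) × Bin(j; 52, 0.02).

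- 20% v 2%: power 0.803.
- 2% v 2%: size 0.00042, which rounds to the stated 0.0004.
- One-sided: power 0.897, size 0.0014, which does not match.

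So a two-sided, between-arm Fisher test was sized.

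**Step 2. A general mild loss.** The documents give no SD for percent change. Assume normal percent change, mean zero on saline, and a uniform fall of d points on lidocaine. Then

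- saline rate = Φ(−19.5/SD); lidocaine rate = Φ(−(19.5 − d)/SD);
- Fisher power by enumeration, as in step 1;
- continuous power from an unadjusted two-sample t test of percent change, noncentrality (d/SD) × √(52/2), 102 df.

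If the 2% is the saline rate of falls of at least 19.5%, SD = 19.5/2.054 = 9.49. That link is an assumption, so SDs of 15 and 20 are shown too. For d = 5:

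| SD | Saline rate | Lidocaine rate | Noncentrality | Fisher | Continuous |
|---|---|---|---|---|---|
| 9.49 | 2.0% | 6.3% | 2.69 | 0.045 | 0.758 |
| 15 | 9.7% | 16.7% | 1.70 | 0.11 | 0.39 |
| 20 | 16.5% | 23.4% | 1.27 | 0.10 | 0.24 |

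At SD 9.49, falls of 7.5 and 10 points give Fisher 0.227 and 0.592, continuous 0.979 and above 0.99.

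**Step 3. A marked block in a few patients.** This is closer to the Power Analysis assumption. Keep SD 9.49 and give a subgroup of lidocaine patients a block of 25 to 60 points, with the subgroup size set so that the rates are 20% v 2%. By simulation, continuous power is 0.72 to 0.88 and Fisher about 0.80. Neither test is consistently better.

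**Step 4. What a null Fisher result would mean.** With 1/52 deficits on saline, 8/52 on lidocaine are needed for significance. A result of 6/52 v 1/52 gives p = 0.11. The risk difference is 5/52 = 9.6 points, with Newcombe 95% CI −0.6 to 21.2 points. The p-value alone would hide that range.

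**Step 5. The eight measures.** Suppose a deficit is a fall on any of eight measures, each with an independent 2% false-positive rate, and lidocaine adds a true deficit in 20% of patients (all assumed).

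- Saline: 1 − 0.98^8 = 14.9%.
- Lidocaine: 0.149 + 0.20 × (1 − 0.149) = 31.9%.
- Fisher power: 0.46, against 0.80 planned.

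With latent correlation 0.5 between measures, power is 0.57; with 0.9, it is 0.74.

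**Step 6. What an ANCOVA could detect at 52 per arm.** The difference detectable with 80% power, in SDs of 30-minute strength, is (1.960 + 0.842) × √(1 − r²) × √(2/52). For assumed baseline-to-30-minute correlations r of 0.5, 0.7, 0.8 and 0.9, this is 0.48, 0.39, 0.33 and 0.24 SD.

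**The case against.** The strongest reply is that the plan already answers the main question. The Power Analysis names Fisher's test, two groups, a difference in proportions and alpha 0.05, and the research question names both arms. This stands. A reader might infer from the pre/post wording that no between-arm test is planned, or that the sample size is wrong. The documents do not support either: step 1 reproduces both stated figures as a between-arm test.

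Second, the plan chooses 19.5% as the change that matters, so a supporting ANCOVA may be the reviewer's preference. This stands in part. If the two Primary outcome bullets are one item, Fisher's test is its method and the ANCOVA is an addition, not a missing analysis. A reader might infer that the ANCOVA should replace Fisher's test. Step 3 gives no ground for that, and no section posits the uniform fall behind the large contrasts in step 2. Those powers are also for an unadjusted test of percent change, not for the ANCOVA itself.

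Third, a reader might infer that the number of 30-minute readings is missing because three are specified only at baseline. The Procedure section says measurements are taken before and 30 minutes after, which may mean the same set. The report form in the appendix is not in the text available and may settle it.

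**Conclusion.** The concern holds as a specification gap that should be fixed, with medium confidence. The pre/post sentence does not describe the test that was sized, but the arms can be recovered from other sections, so that part is a wording repair. The more useful change is an analysis of strength on its measured scale, because as written the plan either lists an outcome with no method or leaves losses below 19.5% unaddressed.

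The size of the benefit is uncertain. For a uniform 5-point fall, the continuous test's advantage runs from about 71 percentage points of power (SD 9.5) to about 15 (SD 20). It may vanish for a block confined to about 20% of patients. All of this rests on normal percent change and on SDs that the documents do not give.

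The 80% power for Fisher's test carries over only if the 20% and 2% rates refer to the 19.5% threshold and to whatever per-patient rule is chosen. The Power Analysis speaks of a motor deficit and never ties it to 19.5%.

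**What to change.** 1. **Main strength analysis.** Replace the sentence with: the proportion of patients with a decrease of at least 19.5% from baseline to 30 minutes, lidocaine versus saline, by two-sided Fisher's exact test, with risk difference and 95% CI. Reword null hypothesis 1 as lidocaine versus saline. State that the 20% and 2% rates refer to this definition, or recheck the power. Treat within-arm change as descriptive.
2. **Supporting analysis.** Add an ANCOVA of 30-minute strength on arm and baseline strength, with adjusted difference and 95% CI.
3. **Analysed value.** Before unblinding, state how the eight measures and their repeat readings form the value used in items 1 and 2. The sponsor should choose the rule. A rule of the any-of-eight kind would require 52 per arm to be rechecked.

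Separately, the Data Analysis Plan says "The primary outcome will be the proportion of participants with 50% or greater reduction in neck and arm pain on the NRS pain score", assessed at 1 month. That conflict is its own issue, but it must be reconciled before the strength test is called confirmatory.

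Cost: wording and a little more analysis. Baseline and 30-minute strength are already planned, so no visit or measurement is added. The sample size is unchanged if the condition in item 1 holds. The downside is that the ANCOVA may add little if the effect is confined to a few patients.

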**Introduction**

Cervical radicular pain is a common problem that is often treated by epidural steroid injection (1). While clinical practice guidelines do not specifically recommend or discourage the use of local anesthetic in the epidural injectate (2), the majority of the published literature on clinical outcomes of cervical epidural steroid injection includes the use of lidocaine in the epidural injectate (3-11). Consequently, many practitioners elect to use local anesthetic in the epidural injectate in order to obtain additional diagnostic information when the precise source of pain is not clear from clinical presentation and imaging. Local anesthetic may also be included in order to provide immediate pain relief in cases of painful acute radicular symptoms.

Local anesthetic injection into the epidural space has the potential to cause transient weakness of the upper extremities. High dose local anesthetic in the cervical epidural space (12) and inappropriately placed low-dose local anesthetic in the subdural space or subarachnoid space (13, 14) are known to cause motor weakness. Appropriately placed, low-dose local anesthetic injected into the epidural space via a transforaminal approach, in close proximity to the exiting spinal nerve root, causes motor block in a small proportion of patients (15). However, the effect of low-dose injection of local anesthetic in the cervical interlaminar epidural space on objective upper extremity strength has not been characterized in the published literature. This proposition affects post-procedure instructions, as even mild weakness may pose a hazard during performance manual activities that require the upper extremity/extremities such as using a handrail or cane handle for support.

Dynamometry is an established and validated method for assessing muscle strength and motor neuron function with high reliability, and has been used to objectively assess changes in upper extremity strength.

This study aims to determine whether a standard dose of 2 mL 1% lidocaine included as a steroid diluent in a C7-T1 cervical interlaminar epidural steroid injection (CESI) causes an objective change in strength as measured by dynamometry. We hypothesized that cervical epidural lidocaine will cause an objective decrease in strength in functional movements of the upper extremity.

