### **Significance:**

Cervical radicular pain is relatively common, often treated with epidural steroid injection (ESI), when conservative treatments like oral analgesics, physical therapy, and activity modification have failed. There are no universal clinical practice guidelines for the use of diluents when CESI are performed.

Interlaminar CESI may be performed with or without the use of local anesthetics, due to training bias or theoretical concerns of weakness. CESI without the benefit of local anesthetic as a steroid diluent increases the latency of pain relief and may decrease diagnostic information immediately after a CESI with regard to pain generators responsible for symptoms, and may potentially decrease patient satisfaction.

By evaluating the effects of local anesthetic as a diluent during interlaminar cervical ESI, we will enhance the safety of this treatment with regard to expectations of objective motor weakness as well as post procedure pain control in the recovery phase after the injection procedure.

Additionally, investigation of short-term pain, function, medication use, and global impression of change following use of local anesthetic versus saline as a diluent during interlaminar cervical ESI will provide evidence to inform the optimization of clinical outcomes related to steroid diluent choice.

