### **Procedure**

All patients evaluated in the University of Utah Orthopaedic Center who will have a CESI with triamcinolone will be considered for participation in the study. Subjects will be consented for participation in the study and informed consent will be obtained. Each subject will be randomized into a group assignment in a 1:1 manner, #1 or #2, as outlined in the Methods section above. All documentation will be stored using a unique coded identifier to ensure compliance with HIPPA.

A Report Form will be used to record all pre- and post-procedure data (See Appendix)

In every participant in Control Cohort, Group 1 and Group 2, a pre-procedure NRS pain score, pain medication use, and presence of subjective or objective symptoms of UE weakness will be recorded. Bilateral handgrip, wrist extension, elbow flexion, and elbow extension strength (myotomes C5-T1) will be measured by a trained research assistant prior to the injection procedure using a handheld JAMAR® PLUS+ digital dynamometer (Sammons Preston, Bollingbrook, IL) for hand grip strength and a Lafayette Manual Muscle Testing System model 01163 (Lafayette Instrument Company, Lafayette, IN) for arm strength assessment. Three baseline strength measurements will be recorded for each strength test (20,21). Validation studies using similar protocols for upper extremity functional strength measurement show a high degree

of test-retest reliability with a narrow range of variability [22–26]. Additionally, light touch and pinprick sensory testing in the C5-T1 dermatomes will be performed with a tapered whisp of cotton and a disposable safety pin, respectively, in accordance with the methods described when performing an American Spinal Injury Association (ASIA) examination in accordance with the international standards for neurological classification of spinal cord injury (27).

Measurements will be taken prior to and 30 minutes following the injection procedure. Participants in Group #1 and Group #2 will also be queried with the Upper Extremity Functional Index (UEFI) before the injection procedure and again 1 day after the procedure (administered via telephone).

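### Strength is analysed by Fisher's exact test alone, with no effect estimate or confidence interval, so a non-significant result cannot be told apart as reassuring or inconclusive

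*Combined protocol and SAP*

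**What the plan says.** The Statistical analysis section states that "Differences in strength as measured by dynamometry pre-and post-injection will be assessed by Fishers exact test". The only descriptive statistics it plans are means and standard deviations for demographics, pain and UEFI scores; strength is not among them. The Primary outcome section lists each individual's change in strength by group and a categorical analysis at a 19.5% change, but names no effect measure. The heading Interpretation of Anticipated Results is followed directly by the Statistical analysis heading, with no text on how a result will be read.

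The first null hypothesis is that injections with local anesthetic "have no effect on objective upper extremity strength following the injection". The Significance section says of the trial that "we will enhance the safety of this treatment with regard to expectations of objective motor weakness", and the Introduction links the question to post-procedure instructions, because even mild weakness may be hazardous when an arm is needed for support.

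The Power Analysis claims power above 80% with 52 per arm. It puts the deficit rate on lidocaine at 20%, and for the comparator it supposes that "those in the Saline group will demonstrate no difference in motor strength after the CESI, assuming a 2% measurement error". Alpha is 0.05 and the achieved level is given as 0.0004.

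**The concern.** Fisher's test answers whether the data are incompatible with equal proportions. It does not say how large an excess of weakness the data still allow. Deficit counts near zero are expected in the saline arm, so a non-significant result may mean that little excess weakness is plausible, or that the excess the trial was sized to detect remains plausible. The planned output is the same in both cases, and nothing in the plan tells the analyst to separate them.

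That matters more for a harm question than for an ordinary efficacy comparison. Combined with a null hypothesis of no effect and a stated safety purpose, p > 0.05 could be taken as evidence that strength is unaffected when the result is inconclusive.

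**Working it through.** **Inputs.** 52 per arm, lidocaine 20%, alpha 0.05 and achieved level 0.0004, all from the Power Analysis. Allocation is 1:1 (Procedure section). Two inputs are inferred: saline 2%, from the measurement-error clause, and a two-sided test, since sidedness is not stated.

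**1. Reproduce the plan's figures.** Take all tables with x deficits of 52 on lidocaine and y of 52 on saline.

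Power = Σ Bin(x; 52, 0.20) × Bin(y; 52, 0.02) over tables with Fisher p ≤ 0.05 = 0.803.

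With both rates at 2%, the same sum is 0.00042. Both stated figures (> 80% and 0.0004) therefore reproduce. One-sided 0.05 gives power 0.897 and size 0.0014. Saline at 0% gives power 0.963. Of the variants tried, only two-sided with 2% in saline matches both figures, so the design difference is 20 - 2 = 18 points.

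**2. One result by hand: 4/52 v 0/52.**

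- Fisher p = 2 × C(52,4)/C(104,4) = 2 × 270,725/4,598,126 = 0.118.
- Wilson limits for x/n are [x + z²/2 ± z√(x(n - x)/n + z²/4)]/(n + z²), with z = 1.96. For 4/52: 3.03% to 18.17%. For 0/52: 0% to 6.88%.
- Difference: 4/52 - 0/52 = 7.69 points.
- Newcombe lower limit: 7.69 - √[(7.69 - 3.03)² + (6.88 - 0)²] = -0.6.
- Newcombe upper limit: 7.69 + √[(18.17 - 7.69)² + (0 - 0)²] = 18.2.

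**3. Other non-significant results by the same formulas.**

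| Lidocaine v saline | Fisher p | Difference (points) | 95% interval | 18 points excluded? |
|---|---|---|---|---|
| 1/52 v 1/52 | 1.000 | 0.0 | -8.3 to 8.3 | yes |
| 3/52 v 0/52 | 0.243 | 5.8 | -2.1 to 15.6 | yes |
| 4/52 v 0/52 | 0.118 | 7.7 | -0.6 to 18.2 | no |
| 5/52 v 0/52 | 0.057 | 9.6 | 0.8 to 20.6 | no |
| 6/52 v 1/52 | 0.112 | 9.6 | -0.6 to 21.2 | no |
| 7/52 v 1/52 | 0.060 | 11.5 | 0.9 to 23.5 | no |
| 9/52 v 2/52 | 0.052 | 13.5 | 1.4 to 26.2 | no |

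With no saline deficits, significance needs 6/52 (p = 0.027). Miettinen-Nurminen upper limits agree with the Newcombe upper limits to within 0.5 points.

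**4. How often the ambiguous case arises.** Sum the table probabilities over results with p > 0.05 and a Newcombe upper limit of 18 points or more.

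| True rates, lidocaine v saline | Non-significant | Non-significant and upper limit ≥ 18 points |
|---|---|---|
| 20% v 2% (design) | 19.7% | 17.6% |
| 10% v 2% (assumption made here) | 79.2% | 39.2% |
| 2% v 2% | almost all (1 - 0.0004) | 0.8% |
| 20% v 0% (saline read as zero) | 3.7% | 3.3% |

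At the design rates, 17.6/19.7 = 89% of non-significant trials leave 18 points inside the interval. When both rates are 2%, the upper limit is below 18 points in about 99% of trials, so a harmless diluent could show itself as such at the planned size.

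**The case against.** This is a superiority design. The Introduction hypothesises that lidocaine will reduce strength, and the trial has its stated power for its stated effect. The null hypothesis is conventional, and failing to reject it is not accepting it. A reader might infer that the plan will declare no effect, or relax precautions, whenever p > 0.05. Nowhere does the document say so. The risk is that a bare p-value *could* be read that way, because no interpretation is given. This part of the objection stands and limits the claim.

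Fisher's test also needs the deficit count in each arm, and anyone shown those counts can compute an interval. That is true, but the plan does not commit to reporting the counts, and an interval method chosen after the data are seen carries less weight.

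A reader might also infer that 20% is too optimistic, since the Introduction mentions motor block in a small proportion of patients after transforaminal injection. The documents do not support that. The reference list shows the cited source to be a lumbosacral adverse-event study, whereas the 20% is attributed to earlier strength observations, listed as a preliminary study of cervical interlaminar injection with low-dose lidocaine. Neither source can be checked here. The 10% v 2% row is therefore only an illustration.

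Finally, score-type intervals do not match Fisher's test: at 5/52 v 0/52, p = 0.057 but the Newcombe interval excludes zero. That is a fair criticism of leaving the method open. It is met by naming one method and acknowledging the discrepancy.

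**Conclusion.** The concern holds as a gap in reporting and interpretation. The sample size is not wrong and Fisher's test is not invalid. The planned strength analysis cannot separate results such as 4/52 v 0/52, which leave the design difference open, from results such as 1/52 v 1/52, which exclude it. At the design rates, 17.6% of trials would fall in the first group.

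This rests on 52 analysed per arm, a two-sided test, Newcombe intervals and saline at 2%. If saline is taken as 0%, the design difference becomes 20 points. Then 4/52 v 0/52 (upper limit 18.2) excludes it, and the ambiguity starts at 5/52 v 0/52 (20.6). It also becomes rarer: at true rates of 20% v 0%, 2.3% of trials are non-significant with an upper limit of 20 points or more.

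A reader might take 18 points as a safety margin, or as the loosest acceptable one. The documents give no basis for that. It is only the difference the trial was sized to detect, and an interval that excludes it does not show that smaller excesses are unimportant: 3/52 v 0/52 has an upper limit of 15.6 points.

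**What to change.** In the Statistical analysis section, before unblinding:

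- Keep Fisher's exact test.
- Report, for each arm, the number and proportion of participants with a strength loss of 19.5% or more.
- Report the risk difference, lidocaine minus saline, with a 95% confidence interval by one named method, preferably exact. If a score-type interval such as Newcombe is chosen, state that it can disagree with Fisher's test near the boundary.
- State that a non-significant result will be interpreted from the upper confidence limit, and will not be reported as absence of weakness while the interval still includes the 18-point difference the trial was designed to detect.

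A formal non-inferiority margin is optional. If the sponsor wants one, it is the sponsor's to choose and justify.

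The risk difference also needs a participant-level event. The plan does not say how the bilateral tests (four movements on each side, eight in all) combine into one deficit, and the Data Analysis Plan names a different primary outcome (pain at 1 month). Both are separate matters to settle alongside this one.

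The cost is a few lines of SAP text and one added output, with no change in sample size or data collection. The downside is that some null results will have to be called inconclusive.
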